#### Children

- Growth disturbance due to insufficient secretion of growth hormone (GH) and growth disturbance associated with Turner syndrome and chronic renal insufficiency.
- Growth disturbance (current height standard deviation score (SDS) < -2.5 and parental adjusted SDS < -1) in short children born small for gestational age (SGA), with a birth weight and/or length below -2 standard deviation (SD), who failed to show catch-up growth (height velocity (HV) SDS <0 during the last year) by 4 years of age or later.
- Prader-Willi syndrome (PWS) for improvement of growth and body composition. The diagnosis PWS should be confirmed by appropriate genetic testing.

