## 5 Population

The study population will consist of a representative group of children of both sexes, aged  $\geq 4$ , with short stature born small for gestational age (SGA).

SGA is defined as per the label indication authorised by the EMEA:

“Growth disturbance (current height standard deviation score (SDS)  $< -2.5$  and parental adjusted SDS  $< -1$ ) in short children born small for gestational age (SGA), with a birth weight and/or length below -2 standard deviation (SD), who failed to show catch-up growth (height velocity (HV) SDS  $< 0$  during the last year) by 4 years of age or later.”

Standardized and controlled Enrolment Authorization:

To assist Investigators to avoid errors in the local calculation of the auxological parameters by applying different ways of calculation and to ensure that only patients in strict adherence to the SGA definition in the study protocol are enrolled, a standardized and controlled procedure for patient enrolment authorization (“Enrolment Authorization Fax”) was implemented after the first 60 patients were enrolled in the study (by November 2008).

For the patients enrolled before implementation of the “Enrolment Authorization Fax” a standardized approach for the recalculation of growth indication for inclusion according to inclusion criteria 2, 3 and 5 was implemented in March 2009.

Historical data will be used to screen the subjects for eligibility, i.e. records of birth length and weight, as well as height and weight measurements taken 1 year (between 18 months and 6 months) before the start of GH treatment for calculation of HVSDS. For the evaluation of gestational age, the date of the last menstrual period will be used, however, if this is not known, ultrasonographic data obtained during the pregnancy may be used.

The study will be performed in approximately 40 centres in Europe. The treating physicians shall be appropriately qualified and experienced in the diagnosis and management of SGA. The patients will be treated as out-patients.

[REDACTED] Subjects dropping out before completing 1 year of treatment will be replaced.

[REDACTED]

[REDACTED]

[REDACTED]

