### 5.1.1 Inclusion criteria

1. Pre-pubertal (Tanner stage I) children born SGA  
Boys:  $\geq 4$  years of age (bilateral testicular volume  $< 4$  ml)  
Girls:  $\geq 4$  years of age (bilateral Tanner breast stage 1)
2. Growth disturbance defined as current height SDS  $< -2.5$  (and parental adjusted SDS  $< -1$ ) for chronological age and sex according to country specific references. If country specific references are not available, pre-defined published references will be used.
3. Birth weight and/or length below -2 SD for gestational age (according to country specific references). For the evaluation of gestational age, the date of the last menstrual period or ultrasonographic data obtained during the pregnancy should be used. If country specific references are not available, pre-defined procedures / published references will be used.
4. Height records between 18 months and 6 months prior to the start of GH treatment must be available
5. Calculated height velocity SDS  $< 0$  during the last year according to [Prader \(1989\)](#).
6. Written informed consent of patient (for children who can read and write) and parent or legal guardian

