### **10.5 Analysis of efficacy endpoints**

#### **10.5.1 Auxological endpoints**

These are height, height SDS, height velocity and height velocity SDS. These parameters will be monitored at baseline, at every 3 months during GH treatment and at the end of treatment. The effectiveness of treatment in inducing growth will be determined by descriptive statistics of the height at each scheduled visit including a comparison to the height at baseline. Similar analyses will be conducted for the height SDS.

The effectiveness of treatment in accelerating linear growth rate will be determined by analyzing the annual height velocity in cm/year (the difference between two height measurements divided by the time interval between these two measurements multiplied by 365.25) at each scheduled visit and by comparing it to the height velocity determined at baseline using historical data. Similar analyses will be conducted for the height velocity SDS.

Treatment will be considered to be ineffective (leading to drug discontinuation) if HVSDS remains below +1 in the first year of treatment.

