### **Body height and derived parameters**

Patients' body height is determined at each visit. The three other primary endpoints are calculated using the recorded height measurements. HV will be calculated in cm/year as the difference between two height measurements divided by the time interval (in days) between these two measurements and multiplied by 365.25. Patients' body height at start of treatment serves as baseline value for calculating HV at month 3, 6, 9 and 12. From the 15-months-visit onwards, the baseline value for HV calculation will be patients' body height at the visit dating back 12 month in the past, e.g., height after 3 months will serve as baseline value to determine HV at 15-months-visit, height after 6 months will serve as baseline to determine HV at 18-months-visit, and so on ("moving 12-months HV basis").

HV and HV SDS for the baseline visit are calculated using historical height data. All corresponding values are recorded in the CRF. The historical reference values to assess the height velocity at screening (V0) and baseline (V1) will be assessed as follows: The historical value, which was assessed next to day 365 prior to height assessment at baseline, will be selected. If there are two values, one assessed x days prior to day 365 and one assessed x days after day 365, the one assessed longer ago will be selected. Derived height velocity values will be rounded to two digits. If for any historical height assessments, the assessment date was given partial only, the 15th of the respective month will be used. If in the final data negative HV values are assessed, this will be set to 0 for analysis.

Height and height velocity will also be expressed in SDS. SDS reflects the deviation of a measured value from the mean value of normally growing children of the same sex and chronological age, expressed in units of the standard deviation of normally growing children of the same sex and chronological age.

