**TABLE 14.2-1.8.1 ANALYSIS OF MEAN CHANGE FROM BASELINE IN HV SDS (CS) BY COMPLETERS, TOTAL AND VISIT (FAS)**

See shell for TABLE 14.2-1.2.1 ANALYSIS OF MEAN CHANGE FROM BASELINE IN HEIGHT BY COMPLETERS, TOTAL AND VISIT (FAS).

Programming note: Please add one column 'Status' (value: Completers, Total) before column Visit.

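### The Month 12 change from baseline in height velocity SDS includes some regression to the mean, because entry to the study required nearly the same velocity to be below 0 SDS

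*Protocol*

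**What the plan says.** Protocol 10.5.1 assesses acceleration of growth in two ways: by analysing annual HV at each scheduled visit, and "by comparing it to the height velocity determined at baseline using historical data". HV SDS is handled in the same way. SAP 4.6.1 adds a 95% confidence interval for the mean difference from baseline at each later visit. For HV SDS these results are in Tables 14.2-1.8.x (cross-sectional reference) and 14.2-1.10.x (peak-centred reference).

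Four further points fix what the baseline is.

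- **Entry rule.** Inclusion criterion 5 (Protocol 5.1.1) requires "Calculated height velocity SDS $< 0$ during the last year according to" the cited Swiss growth reference.
- **Data behind the entry rule.** Protocol section 5 takes "height and weight measurements taken 1 year (between 18 months and 6 months) before the start of GH treatment for calculation of HVSDS".
- **Data behind the analysis baseline.** The SAP, under Body height and derived parameters, states: "HV and HV SDS for the baseline visit are calculated using historical height data". It then specifies which height: "The historical value, which was assessed next to day 365 prior to height assessment at baseline, will be selected".
- **Comparator.** Protocol sections 4 and 6.2 describe a non-comparative study with a single treatment group.

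Neither document mentions regression to the mean, a second pre-treatment velocity, or an untreated comparator for HV.

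**The concern.** A velocity calculated from two heights about a year apart varies from year to year within a child. If children are admitted only when this value is below 0 SDS, those whose velocity happened to be low that year are over-represented. Their velocity would be expected to rise at the next measurement even without treatment.

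In a single-arm study, the mean change from that baseline is then treatment effect plus this rise, and the confidence interval is centred on the sum. The protocol presents the comparison as a means of determining effectiveness, so a reader of the HV SDS change tables would take the whole change as growth gained on treatment. At stake is how large the reported gain in HV SDS is, within a secondary and descriptive efficacy objective.

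**Working it through.** The plan gives no effect size, SD or power for the HV comparison, and no formal sample size calculation was made (Protocol 10.7). There is no figure to reproduce.

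**Step 1. Are the entry velocity and the baseline velocity the same quantity?** Both start from a historical height. The entry velocity uses one taken 6 to 18 months before treatment; the baseline velocity uses the one nearest 365 days before the baseline height. The entry velocity is judged at screening, up to 8 weeks before Visit 01 (Protocol 7.1.1). The baseline velocity ends at Visit 01 (SAP 4.1), or at screening if there was no Visit 01. They are nearly, but not exactly, the same.

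**Step 2. Expected change with no treatment effect.** These are assumptions, not document values: HV SDS in the eligible pool is normal with mean μ and SD 1; selection is HV SDS below 0; the correlation between the pre-treatment and first-year velocities is ρ. With λ = φ(−μ)/Φ(−μ):

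- mean baseline after selection = μ − λ
- expected untreated change = (1 − ρ)λ

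| μ | λ | Mean baseline | Change, ρ = 0.2 | Change, ρ = 0.5 | Change, ρ = 0.8 |
|---|---|---|---|---|---|
| 0 | 0.798 | −0.80 | +0.64 | +0.40 | +0.16 |
| −0.5 | 0.509 | −1.01 | +0.41 | +0.25 | +0.10 |
| −1.0 | 0.288 | −1.29 | +0.23 | +0.14 | +0.06 |

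For example, with μ = −0.5 and ρ = 0.5, the change is 0.5 × 0.509 = 0.25. The change is positive whenever ρ is below 1.

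**Step 3. Size relative to the planned interval.** Under the same model, the SD of the change is √[(1 − ρ)²v + 1 − ρ²], where v = 1 + μλ − λ². With μ = −0.5 and ρ = 0.5, v = 0.486 and the SD is √(0.25 × 0.486 + 0.75) = 0.934. With all 278 enrolled patients contributing, the 95% half-width is 1.96 × 0.934/√278 = 0.11. Over the grid above the half-width is 0.07 to 0.14. With no treatment effect, the interval would lie above 0 with probability about 0.99 or more for μ = 0, 0.79 to above 0.99 for μ = −0.5, and 0.34 to 0.91 for μ = −1.

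**Step 4. Does the gap between screening and Visit 01 matter?** In a simulation of one million draws per scenario, selection was made at screening and the baseline was taken 8 weeks later from the same historical height. For ρ = 0.2, 0.5 and 0.8 the change was +0.60, +0.38 and +0.16 at μ = 0, and +0.39, +0.25 and +0.10 at μ = −0.5. Adding height measurement error (assumed SD 0.3 of one annual-HV SD) raised these somewhat, for instance from +0.38 to +0.42. Between 4% and 17% of baseline values were at or above 0.

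**Step 5. Where does the untreated Month 12 mean sit relative to 0?** It is the baseline mean plus the change. Over the grid it runs from −0.80 + 0.64 = −0.16 to −1.29 + 0.06 = −1.23. It is below 0 throughout, so comparing the on-treatment mean with 0 does not credit this artefact to treatment.

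**The case against.** The strongest reply is that little is at risk. Protocol 10.5.1 looks at the on-treatment velocity as well as the change. Mean HV SDS with confidence limits is already in Tables 14.2-1.7.1 and 14.2-1.9.1, and the change in height SDS is in Table 14.2-1.4.1. The ratio of change in height age to change in chronological age, and the first-year benchmark of +1, do not use baseline velocity. Efficacy is secondary and summarised descriptively. All of this stands, and it limits the point to which result carries the statement on acceleration.

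Several stronger readings are tempting but unsupported.

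- **That the gain is mostly artefact.** The protocol's response benchmark is +1 on treatment, while the modelled baseline mean is −0.80 to −1.29. A child moving from that mean to the benchmark gains about 1.80 to 2.29 SDS, well above 0.64. The background (Protocol 1.2.3) reports a height gain of 0.2 SD over 6 years untreated, against 2.0 to 2.7 SD with continuous treatment. It does not say whether those children were selected on velocity.
- **That every baseline value is below 0.** The rule binds at screening. A minority of Visit 01 values can be at or above 0, although the mean bias hardly changes.
- **That raw HV in cm/year is biased upward at all visits.** The calculation is in SDS and concerns the first year. Treatment continues until velocity falls below 2 cm/year, so late changes in raw velocity reflect age and completion of growth.
- **That a coverage probability can be attached to the interval, or that very short baseline intervals dominate.** Coverage depends on a bias and an SD that the documents do not give. Six months is the permitted extreme; the SAP picks the height nearest day 365, and Table 14.1-12 will show the intervals actually used.

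**Conclusion.** The concern holds for the early change from baseline in HV SDS, at Month 12, in Tables 14.2-1.8.x and 14.2-1.10.x. The direction follows from the design: selection on nearly the baseline variable, imperfect year-to-year correlation and no control arm. The size cannot be identified from the documents. About +0.06 to +0.64 SDS is a range over assumptions (normal distribution, SD 1, pool mean 0 to −1, correlation 0.2 to 0.8), not an estimate. In most of those scenarios it exceeds the half-width of the planned interval, so it matters for the reported size of the gain. The conclusion that treated children grew faster does not depend on this change alone, and the primary diabetes endpoint is unaffected. This is a cheap improvement to a secondary analysis.

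**What to change.** In SAP 4.6.1:

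1. Base the statement on growth acceleration on mean on-treatment HV SDS at Month 12 with its 95% confidence interval against 0 (Tables 14.2-1.7.1 and 14.2-1.9.1), together with the change in height SDS (Table 14.2-1.4.1). Height SDS was also an entry criterion, so the same reasoning applies to it in principle; the small untreated change reported in the protocol's background suggests that the effect there is minor.
2. Do not use visits after Month 12 for this statement. Children with first-year HV SDS below +1 are to be discontinued (Protocol 6.5.9), so later means come from a group selected upward on the same variable. The cross-sectional reference also takes no account of individual pubertal timing (SAP, HV SDS CS).
3. Keep the change-from-baseline HV SDS tables as descriptive, with a footnote that baseline HV SDS was selected below 0 at screening and that the change includes regression to the mean.
4. A row adjusted for regression to the mean is optional. If printed, label it a sensitivity analysis and state the assumed mean, SD and correlation, since the documents supply none of them.

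The cost is a few sentences and one footnote, with no new data. The downside is a smaller headline figure: a gain measured from 0 is lower than one measured from the selected baseline by the distance of that baseline below 0, which is 0.80 to 1.29 SDS in the model.

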### **10.5.2 Pharmacodynamic endpoints**

These are IGF-I and IGFBP-3 serum levels, which will be assessed at baseline, at 3, 6, 9 and 12 months, then bi-annually during treatment, and at the end of treatment.

The effect of treatment on serum IGF-I and IGFBP-3 levels will be evaluated using descriptive statistics for the observed values at each visit together with the absolute and relative changes as compared to baseline.

### **10.6 Interim analysis**

Interim analyses are planned at the following time points:

- Q4/2011 with data of patients who completed 1 year of treatment
- Q4/2012 with data of patients who completed 2 years of treatment
- Q4/2020 with data of patients who finished treatment

Additional *ad-hoc* interim analyses will be performed in case needed for interactions with health authorities.

### **10.7 Sample size calculation**

There was no formal sample size calculation for this study which is intended to exploratorily investigate the long-term effect of the treatment with respect to the development of diabetes. No such incidences are currently available to allow for a rigorous sample size estimation. Results obtained in this study will be compared to data published in the literature.

200 subjects were agreed upon during the discussion with the EMEA. Taking into account a drop-out rate of 20%, 240 patients will be included in the study. Subjects dropping out before completing 1 year of treatment will be replaced.

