### **6.5.9 Study drug discontinuation**

Treatment can be terminated at any time, at the discretion of the investigator or the Sponsor, or at the patient's request, in the event of an AE or due to treatment failure.

Study drug treatment has to be discontinued in the following cases during treatment period:

- Occurrence of overt diabetes mellitus; defined as fasting blood glucose  $\geq 126$  mg/dl or  $\geq 7.0$  mmol/l and abnormal findings in OGTT defined by  $\geq 200$  mg/dl or  $\geq 11.1$  mmol/l after 120 minutes. For further instruction see appendix
- Requirement of an increase of the recommended dose to obtain increased growth velocity
- Renal transplantation
- Diagnosis of benign intracranial hypertension
- Malignancy
- Pregnancy
- Withdrawal of informed consent
- Treatment failure

Treatment failure is defined as: Inadequate response to treatment, e.g. height velocity standard deviation score (HVSDS) below +1 in the first year.

Furthermore a standardized controlled procedure for the calculation of the treatment response (via "Treatment Response Control Fax") was implemented (see also 6.5.3 treatment duration) to ensure a unified flawless computation and to authorize treatment continuation, if applicable (managed by Data Management at Metronomia). In case the Investigator does not agree with the assessment by Data Management, Sandoz is informed and initiates the re-assessment of the treatment response data via an independent specialist reader.

Patients who are withdrawn from the study before completing at least one year of treatment with Omnitrope® will be replaced.

Study drug must be discontinued if the investigator concludes that continuation would result in significant safety risk for that patient and in the event of pregnancy.

Patients who discontinue study drug before completing the study should not be considered withdrawn from the study and should be scheduled for a final visit as soon as possible, at which time all of the assessments for the final visit will be performed.

A Study Drug Discontinuation form should be completed, giving the date and reason for stopping the study drug. All patients who discontinue study drug, including those who refuse to return for a final visit, will be contacted for safety evaluations during the 4 weeks following the last dose of the study drug.

Patients who discontinued this study for any reason will not be able to re-enter the study.

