### **10.1.2 Full analysis set**

The full analysis set (FAS) will follow the intent-to-treat-principle and therefore consists of all patients who received at least one dose of study medication.

The assignment of the patients to the respective analysis set will be done prior to each interim and to the final analysis during a specific data review meeting.

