## 2.5 Determination of sample size

There was no formal sample size calculation for this study which is intended to exploratorily investigate the long-term effect of the treatment with respect to the development of diabetes. No such incidences are currently available to allow for a rigorous sample size estimation. Results obtained in this study will be compared to data published in the literature.

[REDACTED]  
Patients dropping out before completing 1 year of treatment will be replaced.

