**TABLE 14.1-2 PATIENT ENROLMENT**

Site code	SCR	Number of patients*												
		V01	V02	V03	V04	V05	V06	V07	V08	V09	V10	V11	...	
		M0	M3	M6	M9	M12	M15	M18	M21	M24	M30	M36		
XXX	XXX	XXX	XXX	XXX	XXX	XXX	XXX	XXX	XXX	XXX	XXX	XXX	XXX	XXX
XXX	XXX	XXX	XXX	XXX	XXX	XXX	XXX	XXX	XXX	XXX	XXX	XXX	XXX	XXX
...	XXX	XXX	XXX	XXX	XXX	XXX	XXX	XXX	XXX	XXX	XXX	XXX	XXX	XXX
Total	XXX	XXX	XXX	XXX	XXX	XXX	XXX	XXX	XXX	XXX	XXX	XXX	XXX	XXX

\* for whom the respective visit was documented or the final visit was assigned to the respective visit  
Note: One patient had only V01 performed, received study medication and was lost to follow-up thereafter. This patient was excluded from the SAF since no information with respect to safety is available.

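### Is 240 too few to leave 200 patients after 20% drop-out?

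*Protocol*

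**What the plan says.** Protocol 10.7 makes no claim to a statistical derivation: "There was no formal sample size calculation for this study". The size comes from a regulatory discussion: "200 subjects were agreed upon during the discussion with the EMEA". The allowance follows at once: "Taking into account a drop-out rate of 20%, 240 patients will be included in the study". The section then closes with the rule that subjects lost before 1 year are replaced.

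The replacement rule appears in three other places:

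- Protocol 5 (Population): "Subjects dropping out before completing 1 year of treatment will be replaced"
- Protocol 6.5.9 (Study drug discontinuation): "Patients who are withdrawn from the study before completing at least one year of treatment with Omnitrope® will be replaced"
- SAP 2.5 (Determination of sample size): "Patients dropping out before completing 1 year of treatment will be replaced"

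None of these ties the rule to the 20%. In the public copies, text beside the rule is redacted in Protocol 5 and SAP 2.5.

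On who is analysed, Protocol 10.1.2 says that the full analysis set "consists of all patients who received at least one dose of study medication". The safety set (Protocol 10.1.1) also asks for one post-baseline safety assessment. The note to SAP Table 14.1-2 describes one patient who was dosed and lost after Visit 01: "This patient was excluded from the SAF since no information with respect to safety is available". The Study status text under Amendment 5 in the protocol reports 278 enrolled, the last on 29-Apr-2010.

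**The concern.** Drop-out occurs among the patients who are included, so an allowance for it is normally found by dividing the number wanted at the end by one minus the drop-out rate. Section 10.7 adds 20% to the starting number instead. On the usual reading, that 200 are meant to remain, the planned enrolment is too small to deliver them at the stated rate.

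The section also puts the 20% next to the replacement rule without saying whether the 20% counts patients who will be replaced, or whether replacements come within the 240 or on top of it.

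At stake would be the only readable justification of the study's size. With no power, effect size or event rate given, 200, 20% and 240 are the only size figures in the section, and the 200 was agreed with a regulator.

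**Working it through.** **Inputs.** Agreed number 200, drop-out 20% and planned inclusion 240 (all Protocol 10.7); actual enrolment 278 (Protocol, Amendment 5, Study status).

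**Reproducing the plan's figure.**

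- Allowance on the starting number: n × (1 + d) = 200 × 1.2 = 240. This matches exactly.
- Allowance on the number included: n / (1 − d) = 200 / 0.8 = 250. This does not match; it is 10 higher.

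So 240 follows from 200 and 20%, but only as 200 plus 20% of 200.

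**What 240 would leave, if 200 is a retained number and no loss is replaced.**

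- Losses at 20%: 0.20 × 240 = 48, against the 40 allowed for.
- Remaining: 240 − 48 = 192, which is 8 below 200 (8 / 200 = 4%).
- Highest drop-out at which 240 still leaves 200: 1 − 200 / 240 = 16.7%.

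**What replacement does.** The documents do not say whether replacements are added to the 240. Assume that they are, and that the 20% includes early losses:

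- If no replacement drops out, 8 are enough: 192 + 8 = 200.
- If 20% of the replacements also drop out, 8 / 0.8 = 10 are needed, so 240 + 10 = 250 patients are included in all.

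Under this assumption 200 are kept if 8 to 10 of the 48 losses fall in the first year and are replaced. If instead the 20% is loss that remains after replacement, 240 leaves 192 as before. The readable text does not decide between the two.

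**What was enrolled.**

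- 278 − 240 = 38 and 278 − 250 = 28, so enrolment passed both figures.
- Counting drop-out over everyone enrolled, 200 remain as long as it does not exceed 1 − 200 / 278 = 28.1%.

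**What the difference would be worth for the primary endpoint.** The SAP gives counts and percentages of patients with diabetes (Table 14.3-3.7) and plans no interval for them, so this is only an illustration. If no case is seen, the exact two-sided 95% upper limit is 1 − 0.025^(1/n):

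| n | Upper limit |
|---|---|
| 192 | 1.90% |
| 200 | 1.83% |
| 240 | 1.53% |
| 250 | 1.46% |
| 278 | 1.32% |

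The gap between 192 and 200, or between 240 and 250, is less than 0.1 percentage point. The diabetes table also uses the safety set, not the patients who remain. The shell of SAP Table 14.3-1.1 gives that set as N=277, one fewer than the 278 enrolled.

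**The case for a change.** The best case for acting is that the wording itself points to 200 as the number remaining: had 200 simply been the number to enrol, an allowance for drop-out would have had no purpose. The absence of a formal calculation excuses the lack of a power statement but not an allowance worked on the wrong base. Replacement does not fully rescue the sentence either, because once replacements are added, 240 is no longer the number included. Protocol version 6.0 also still gives 240 as the plan while reporting 278 enrolled, with no readable account of the extra 38.

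Some of this stands. The allowance was taken on the 200 and not on the number included, and 200 as a retained number is a reasonable inference. It remains an inference, since the section says only that 200 were agreed.

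The step from there to a deficient plan does not stand. The figures of 192 and 250 assume that no loss is replaced, whereas the plan states four times that losses before 1 year are replaced. The missing link between that rule and the 20% may lie in the redacted text, so it cannot be counted as an omission. The practical argument fails too: under Protocol 12.1 any change to the protocol needs a written amendment with sponsor and investigator approval, and this one would revise a recruitment figure almost ten years after the last patient entered.

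**Conclusion.** No change is needed. The plan's 240 is 200 plus 20% of 200. It would be 10 short of 250 only if two conditions hold together: 200 was meant as the number remaining, and none of the 20% is replaced. The first is inferred; the second goes against the stated replacement rule, unless the 20% is meant as loss left after replacement, which no readable text says. A shortfall is therefore possible on one reading but not shown.

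Even on that reading it would be 8 patients in 200, in a single-arm study with no formal size calculation, no power statement and no test of the primary endpoint. Dosed patients who drop out stay in the full analysis set, and the documents show one patient excluded from the safety set, for want of safety data. The 278 enrolled exceed both 240 and 250, so no analysis set, estimate or conclusion depends on which convention was used. If the study report discusses planned size, its authors can describe 240 as 200 plus 20% of 200 without touching the protocol or the SAP.
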